16.2 Sample Size Determination

Based on Simon two-stage minimax design, 13 patients will be enrolled in Stage 1 and evaluated for response. If none of the 13 patients respond (CR or PR), the study will be stopped for futility. Otherwise, the study will proceed to Stage 2 and enroll additional 14 patients for a total of 27 patients. The null hypothesis will be rejected if 4 or more responses are observed among 27 patients. This design achieves 5% type I error and 80% power when the true ORR is 20%

16.3 Statistical Analyses

Demographic and disease characteristics will be summarized using descriptive statistics. Counts and percentages will be used to summarize the distribution of categorical variables. Median, range, mean, and standard deviation will be used for continuous variables. Continuous variables will be tested using Student's t-test and/or Mann-Whitney U test. All statistical tests will be two-sided and $p < 0.05$ will be considered as statistical significance.

The full analysis set will consist of all patients enrolled. The modified full analysis set will consist of all enrolled patients, except patients withdrawn prior to the first efficacy measurement (at Cycle 2). The per-protocol analysis set will consist of all patients from the FU analysis set without any major protocol violations. The safety analysis set will consist of all patients who get treatment regardless of completion of treatment. The safety analysis set will serve as the main analysis set for safety assessments. The modified full analysis set will serve as the main analysis set for efficacy assessments. The efficacy assessment will also be performed on the per-protocol and full analysis sets.

Response rate will be estimated along with corresponding 95% confidence interval using Fisher's exact method. Tumor response (CR, PR, SD, or PD) will be defined according to RECIST v1.1 guideline. Objective response rate (ORR) will be the proportion of patients with a confirmed CR or PR and disease control rate (DCR) is calculated by the proportion of patients with confirmed CR, PR, or SD.

Progression-free survival (PFS) is defined as the time from the date of enrollment to the date that objective progression disease is documented or death due to any cause, whichever occurs first. Overall survival (OS) is defined as the time from the date of enrollment to the date of death. Duration of response is defined as the time from the date of first documented response (CR or PR) until date of documented progression or death in the absence of disease progression.

For PFS and OS, Kaplan-Meier method will be used to estimate survival rates for pre-specified time points along with 95% confidence intervals.

Safety analysis will be include detailed tabulations of adverse events by type, grade and treatment attribution.

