6 STUDY INTERVENTION DISCONTINUATION AND PARTICIPANT DISCONTINUATION/WITHDRAWAL

6.1 Discontinuation of Study Intervention

Discontinuation from nivolumab plus relatlimab does not mean discontinuation from the study, and remaining study procedures should be completed as indicated by the protocol. Patients who received at least 2 doses of the combination treatment will be considered evaluable and the remaining study procedures should be completed as indicated by the protocol in Section 6.2.

If a clinically significant finding is identified (including, but not limited to changes from baseline) after enrollment, the Investigator or qualified designee will determine if any change in participant management is needed. Any new clinically relevant finding will be reported as an adverse event (AE).

The data to be collected at the time of study intervention discontinuation will include the following:

- Progression Free Survival
- Overall Survival
- Adverse events

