6.3 Participant Discontinuation/Withdrawal from the Study

Participants are free to withdraw from participation in the study at any time upon request. An Investigator may discontinue or withdraw a participant from the study for the following reasons:

- Pregnancy
- Significant study intervention non-compliance
- Lost-to-follow up; unable to contact subject
- Any event or medical condition or situation occurs such that continued collection of follow-up study data would not be in the best interest of the participant or might require an additional treatment that would confound the interpretation of the study
- Disease progression which requires discontinuation of the study intervention
- Participant meets an exclusion criterion (either newly developed or not previously recognized) that precludes further study participation
- Participant unable to receive nivolumab and relatlimab combination treatment for 2 cycles over a period of 12 weeks.

The reason for participant discontinuation or withdrawal from the study will be recorded on the Case Report Form (CRF).

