12.5 Definition of disease progression

Progression for patients with measurable disease at baseline is defined as ANY of the following:

- At least a 20% increase in the sum of LD target lesions taking as reference the smallest sum LD recorded since study entry
- In the case where the ONLY target lesion is a solitary pelvic mass measured by physical exam which is not radiographically measurable, a 50% increase in the LD is required taking as reference the smallest LD recorded since study entry
- The appearance of one or more new lesions
- Death due to disease without prior objective documentation of progression
- Global deterioration in health status attributable to the disease requiring a change in therapy without objective evidence of progression
- Unequivocal progression of existing non-target lesions, other than pleural effusions without cytological proof of neoplastic origin, in the opinion of the treating physician (in this circumstance an explanation must be provided)

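### The main ORR set can drop dosed patients who fail before the first scan, and the plan does not fix which 13 and 27 patients the decision rules count

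*Combined protocol and SAP*

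**What the plan says.** **Main set.** Section 16.3 states: "The modified full analysis set will consist of all enrolled patients, except patients withdrawn prior to the first efficacy measurement (at Cycle 2". It adds: "The modified full analysis set will serve as the main analysis set for efficacy assessments". Two other sets are supplementary: "The efficacy assessment will also be performed on the per-protocol and full analysis sets". The full analysis set is everyone enrolled.

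**Response.** Also in 16.3: "Objective response rate (ORR) will be the proportion of patients with a confirmed CR or PR".

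**Decision rule.** Section 16.2 stops the trial after 0 responses in 13. At the end, "The null hypothesis will be rejected if 4 or more responses are observed among 27 patients". Section 1.6 gives type I error 0.0416 and power 0.8011.

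**Leaving the study.** One reason for withdrawal in section 6.3 is "Disease progression which requires discontinuation of the study intervention"; another is a medical condition or situation. Section 12.5 counts as progression "Death due to disease without prior objective documentation of progression", and also global deterioration without objective evidence.

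**Who counts and who is replaced.**
- The Protocol Summary (Target Population) has up to 27 *enrolled*. The Summary (Study Duration) and section 3.1 item 6 have 27 *evaluable*. Section 16.2 has 13 enrolled and evaluated for response.
- Section 6.1: "Patients who received at least 2 doses of the combination treatment will be considered evaluable".
- Section 6.2 removes never-dosed patients from the efficacy analysis and replaces them.
- Section 6.4 replaces treated patients who withdraw or are taken off. Its non-compliance qualifier can be read as covering all of them or only the second group. Section 5.7 makes replacement of non-compliant patients optional.

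**First scan.** Sections 10.2 and 10.8 schedule it at Cycle 3 Day 1. Section 10.3 lists no imaging at Cycle 2.

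**The concern.** A dosed patient who is withdrawn before any post-baseline scan cannot have a confirmed response. Leaving that patient out takes one from the denominator and nothing from the numerator, so the bias can only favour the drug. Nothing in 16.3 limits the exclusion to undosed patients or counts the excluded as non-responders. Section 12.5 gives some of these patients a progression outcome without imaging, but the plan does not say whether that keeps them in the main set.

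The second problem is the decision rule. Its operating characteristics hold for a fixed 13 and a fixed 27, and the documents allow several versions of both. If early failures are dropped and their places refilled, the rule is applied to a favourably selected group, and the chance of a positive verdict rises at every true ORR, including the 5% null. With a threshold of four responses, one or two patients can decide the outcome.

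**Working it through.** **1. The plan's own figures.** Inputs from 1.6 and 16.2: n1 = 13, stop at 0 responses; n = 27, reject at 4 or more; p0 = 0.05, p1 = 0.20.

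P(reject) = Σ over x = 1 to 13 of P(X1 = x) · P(X2 ≥ 4 − x), with X1 ~ Bin(13, p) and X2 ~ Bin(14, p).

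- p = 0.05: terms for x = 1, 2, 3 and x ≥ 4 are 0.01056 + 0.01697 + 0.01097 + 0.00310 = 0.0416.
- p = 0.20: 0.0986 + 0.2150 + 0.2349 + 0.2527 = 0.801.

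Both stated figures reproduce. The sample-size arithmetic is sound for a fixed 27.

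**2. Early failures excluded, not replaced.** The responses among the 13 and the 27 are unchanged, so the count rule keeps 0.0416 and 0.8011. Only the estimate moves. With 4 responses and exact (Clopper-Pearson) 95% intervals:

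| Excluded | ORR | 95% CI |
|---|---|---|
| 0 | 4/27 = 14.8% | 4.2–33.7% |
| 3 | 4/24 = 16.7% | 4.7–37.4% |
| 5 | 4/22 = 18.2% | 5.2–40.3% |

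On average, a true all-treated ORR of 20% is reported as 0.20/(1 − f), where f is the fraction excluded: 22.2%, 23.5% and 25.0% for f = 10, 15 and 20%.

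**3. Early failures excluded and replaced until 27 are evaluable.** All excluded patients are non-responders, so the response rate among those counted is p/(1 − f). The formula in step 1 is evaluated at that rate. The documents give no value for f; 5 to 20% is an assumed range.

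| f | Rate at true 5% | Type I error | Rate at true 20% | Power |
|---|---|---|---|---|
| 0 | 5.0% | 0.0416 | 20.0% | 0.801 |
| 5% | 5.3% | 0.0487 | 21.1% | 0.835 |
| 10% | 5.6% | 0.0573 | 22.2% | 0.866 |
| 15% | 5.9% | 0.0679 | 23.5% | 0.896 |
| 20% | 6.3% | 0.0810 | 25.0% | 0.922 |

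Type I error passes the 5% of section 16.2 at f of about 5.8%. Two replaced among 29 dosed (f = 2/29 = 6.9%) gives 0.052. The chance of stopping after stage 1 at a true 5% is (1 − rate)^13, which falls from 0.513 to 0.476 at f = 10%.

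**4. How often the verdict changes.** Any trial that rejects on the first 27 dosed also rejects on the first 27 evaluable, so disagreement is the difference in P(reject). At f = 10%:
- true ORR 5%: 0.0573 − 0.0416 = 0.016
- true ORR 10%: 0.3393 − 0.2709 = 0.068
- true ORR 20%: 0.8662 − 0.8011 = 0.065

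**5. Is the range of f plausible?** This is an illustration only. Assume exponential survival with medians of 7.6 and 15 months, two of the values cited in section 1.1. Week 8 is about 1.84 months, so the proportion dead by then is 1 − 0.5^(1.84/7.6) = 15% or 1 − 0.5^(1.84/15) = 8%. If every such patient were dropped and replaced, type I error would be about 0.054 to 0.069.

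**The case against.** The strongest reply is that the exclusion of early failures is inferred. Section 16.3 drops only *withdrawn* patients, section 6.1 says that stopping treatment is not leaving the study, and 6.3 only permits withdrawal. Section 12.5 gives an early disease death a progression outcome, so a reader could keep such patients in the set. This stands as far as it goes: the plan permits the exclusion and does not require it. But 6.3 lists progression as a reason for leaving the study itself, and 16.3 has no rule that keeps these patients in.

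The type I error figures need replacement, and no section says in terms that patients who progress or die early are replaced. That is correct. The figures apply only under the broad reading of 6.4, or if the accrual target of 27 evaluable patients is taken literally.

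The Summary and section 3.1 describe stage 1 as testing the treatment on 13 patients and stage 2 as 14 more receiving it, which points to treated patients. That supports the fix, but it conflicts with the main set in 16.3 and does not settle the matter.

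The shift of the lower limit past 5% at 4/22 does not change a verdict. The rule is a count and the test is one-sided; the one-sided 95% lower limit at 4/27 is already 5.2%. The objection is right, and the table in step 2 shows bias in the estimate only.

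The full-set analysis would reveal a divergence. It is not the main analysis, however, and it includes never-dosed patients whom 6.2 removes. Finally, Cycle 3 Day 1 is the end of Cycle 2, so the timing mismatch may be loose wording.

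**Conclusion.** The concern holds. As written, the main ORR set can lose dosed non-responders and cannot lose a responder, and no section fixes the patients to whom 0/13 and 4/27 apply.

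The size depends on replacement. Without it, the decision rule is intact and the bias is confined to the estimate and its interval: 14.8% becomes 16.7% with three exclusions and 18.2% with five. With replacement, type I error rises from 0.0416 to between 0.049 and 0.081 over an assumed 5 to 20% excluded, and at 10% excluded the two readings disagree in 1.6 to 6.8% of trials at true ORRs of 5, 10 and 20%. These results assume that every excluded patient is a non-responder, which follows from the response definition, and an exclusion fraction that the documents do not give. The plan should be corrected, though the design itself is sound.

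**What to change.** - In 16.3, make all patients who receive at least one dose the primary ORR set, and count those without a post-baseline assessment as non-responders.
- Keep the modified set as a sensitivity analysis.
- In 16.2, state that the 0/13 and 4/27 rules apply to the first 13 and first 27 dosed patients.
- For the efficacy count, replace only never-dosed patients.
- Bring 5.7, 6.1, 6.2, 6.4, 16.2 and the Protocol Summary, together with 3.1, into line with this one definition.
- Reconcile the Cycle 2 wording in 16.3 with the Cycle 3 Day 1 scan in 10.2 and 10.8.

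The cost is protocol and SAP wording. The sample size does not change, and 0.0416 and 0.8011 then apply as stated. The reported ORR may be slightly lower.

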1.6 Hypothesis

The null hypothesis is that the true response rate is 5%, it will be tested against a one-sided alternative response rate of 20%. In the first stage, 13 patients will be accrued. If there are no responses in these 13 patients, the study will be stopped. Otherwise, 14 additional patients will be accrued for a total of 27. The null hypothesis will be rejected if 4 or more responses are observed in 27 patients. This design yields a type I error rate of 0.0416 and power of 0.8011 when the true response rate is 20%

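### The ORR estimate and 95% interval in Section 16.3 take no account of the Stage 1 stop: the bias is small, but upper limits are too low at 1 to 3 responses in 27

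*Combined protocol and SAP*

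**What the plan says.** Section 1.6 sets the hypotheses: "The null hypothesis is that the true response rate is 5" per cent, against a "one-sided alternative response rate of 20" per cent. Section 16.2 gives the design: "Based on Simon two-stage minimax design, 13 patients will be enrolled in Stage 1 and evaluated for response". The interim rule is: "If none of the 13 patients respond (CR or PR), the study will be stopped for futility". Otherwise the trial will "enroll additional 14 patients for a total of 27 patients", and "The null hypothesis will be rejected if 4 or more responses are observed among 27 patients". Section 15.5 presents the two-stage design as the rule for stopping for lack of efficacy.

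On estimation, Section 16.3 says "Response rate will be estimated along with corresponding 95% confidence interval" and names Fisher's exact method. It defines ORR as the proportion of patients with a confirmed CR or PR. The main efficacy set is the modified full analysis set. No section names an estimator or interval that allows for the Stage 1 stop.

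**The concern.** A trial reaches Stage 2 only if at least one of the first 13 patients responds. The ordinary proportion and the ordinary exact interval are built for a fixed number of patients, so their usual guarantees (no bias, at least 95% coverage) need not hold here.

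The ORR estimate matters whether or not the null is rejected. Section 1.7.1 plans a comparison with historical PD-1/PD-L1 response data (3.6% in Section 1.1), and Section 1.7.2 says further cohorts may depend on the outcome. The results most affected, 1 to 3 responses in 27, are also likely ones: their probability is 45% at a true ORR of 5% and 47% at 10%.

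**Working it through.** **Inputs.** Stage 1 has 13 patients, with a stop at 0 responses. Stage 2 has 14, for a total of 27, and the null is rejected at 4 or more (Section 16.2). The null and target rates are 5% and 20% (Section 1.6). Assumptions: Fisher's exact method means Clopper-Pearson, and the evaluable numbers are exactly 13 and 27.

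**Step 1: the plan's own figures.** Section 1.6 states: "This design yields a type I error rate of 0.0416 and power of 0.8011 when the true response rate is 20" per cent. Summing P(X1 = x)·P(X2 ≥ 4 − x) over x = 1 to 13 gives 0.0416 at 5% and 0.8011 at 20%, so both reproduce. A single-stage rule of 4 in 27 would give 0.0437 and 0.8177. The test therefore already allows for the Stage 1 stop, whereas the planned estimate and interval do not.

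**Step 2: bias of the crude proportion.** A stopped trial reports 0/13 = 0. Stage 2 responses count only if the trial continues, so the mean is [13p + 14p(1 − (1 − p)^13)]/27 and

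bias = −14p(1 − p)^13/27.

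- p = 5%: 14 × 0.05 × 0.5133/27 = 0.0133, so the mean is 3.7%.
- p = 10%: 14 × 0.10 × 0.2542/27 = 0.0132, so the mean is 8.7%.
- p = 20%: 14 × 0.20 × 0.0550/27 = 0.0057, so the mean is 19.4%.

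The bias is largest at p = 1/14 (about 7%), where it is −(13/14)^13/27 = −1.4 points.

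Among trials that continue, divide the mean by 1 − (1 − p)^13. At 5% this is 0.0367/0.4867 = 7.5%; at 20% it is 0.1943/0.9450 = 20.6%. In that group the bias is upward.

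**Step 3: the unbiased estimate.** For s responses in 27, UMVUE = C(26, s − 1)/[C(27, s) − C(14, s)]. This gives 1/13 = 7.7%, 26/260 = 10.0%, 325/2561 = 12.7% and 2600/16549 = 15.7% for s = 1 to 4.

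**Step 4: the interval.** Rank the outcomes with the 0/13 stop lowest, then by total responses, and invert each tail at 2.5%. For 1/27 the upper limit solves (1 − p)^13 + 13p(1 − p)^26 = 0.025, giving p = 25.1%. For 0/13 it is 1 − 0.025^(1/13) = 24.7% under both methods.

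| Result | Crude, fixed-sample 95% CI | UMVUE, two-stage 95% CI |
|---|---|---|
| 0/13 | 0% (0–24.7) | 0% (0–24.7) |
| 1/27 | 3.7% (0.1–19.0) | 7.7% (0.2–25.1) |
| 2/27 | 7.4% (0.9–24.3) | 10.0% (1.1–27.0) |
| 3/27 | 11.1% (2.4–29.2) | 12.7% (2.5–30.2) |
| 4/27 | 14.8% (4.2–33.7) | 15.7% (4.3–34.1) |
| 5/27 | 18.5% (6.3–38.1) | 19.0% (6.3–38.2) |
| 6/27 | 22.2% (8.6–42.3) | 22.5% (8.6–42.3) |

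From about 8/27 up there is no material difference. Under the fixed-sample method, one response in 27 has a lower upper limit (19.0%) than none in 13 (24.7%).

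**Step 5: coverage over the two-stage outcomes.** At true rates of 2, 5, 10, 15 and 20% the fixed-sample interval covers 98–99%. At 25% it misses 3.8% above and 2.2% below, so coverage is 100 − 3.8 − 2.2 = about 94%. The minimum is 94.0%, and coverage is below 95% only between about 24.8% and 25.4%. The two-stage interval never falls below 95%.

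**The case against.** The strongest case against has four parts.

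*No decision changes.* This stands. The primary test is a count, its error rates already include the stop, and the larger shifts occur at 1 or 2 responses, where the trial is negative under either method.

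*The estimate is not simply biased low.* This also stands. A reader might infer that a reported x/27 understates the ORR on average. That holds only when stopped trials are averaged in, and they are 51% of trials at a true 5%. Among trials that reach 27 the crude proportion is too high, and the UMVUE is higher still: at a true 5% it averages 0.05/0.4867 = 10.3%, against 7.5% crude.

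*The UMVUE is not uniformly better.* Correct. Its root mean squared error is larger at low rates: 4.8 against 3.9 points at a true 3.6%, 5.5 against 4.8 at 5%, and 6.2 against 5.8 at 7%. It is smaller only from about 10% up, by at most about 0.4 points at the rates checked up to 30%. This supports showing both estimates, not replacing one with the other.

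*The interval is not wrong in any gross sense.* A reader might infer from 1/27 that the ordinary interval wrongly rules out the 20% target. At a true 20%, however, 1/27 has probability 0.8%, within the nominal 2.5%, and coverage is 98.1%. The chance of stopping or seeing only one response at 20% is 5.5 + 0.8 = 6.3%, against 1.9% for a fixed sample of 27, but that sum depends on ranking 0/13 below 1/27. What remains is the reversed order of the upper limits at 0/13 and 1/27, and the loss of guaranteed 95% coverage.

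**Conclusion.** The point holds as a modest matter of estimation and reporting. The planned ORR analysis takes no account of the Stage 1 stop. The cost is a bias of at most about 1.4 points averaged over all trials, upper limits 6.1, 2.7 and 1.1 points too low relative to the two-stage interval at 1, 2 and 3 responses (from unrounded limits), and a dip in coverage to 94.0% in a narrow band near a true 25%. At 4/27 the estimate moves by 0.9 points and the limits by at most 0.4; at higher counts the shifts are smaller. The documents give no ground for saying that the design, its type I error, its power or its go/no-go rule is at fault.

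This rests on reading the named method as Clopper-Pearson and on exactly 13 and 27 evaluable patients. Section 16.3 does not say that 27 patients are treated as one fixed sample. That is inferred from the method named and the absence of any adjustment. The two-stage limits also depend on the ordering stated in Step 4.

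**What to change.** In Section 16.3:

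- Replace the fixed-sample interval with one named exact two-stage 95% confidence interval, using stage-wise ordering: the stop at 0/13 ranked lowest, then total responses, as in Jung-Kim. Name a single method, so that no choice is left until the results are known.
- Report the UMVUE alongside the crude proportion, with a note that it is unbiased over both stopping outcomes but has larger mean squared error below a true ORR of about 10%.
- State that both will be computed from the actual Stage 1 and total evaluable numbers if these differ from 13 and 27. This can happen because the modified full analysis set drops early withdrawals and Sections 5.7, 6.2 and 6.4 allow replacement.

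The change needs no extra patients or data. It costs some SAP text, a little more analysis work, and wider upper limits when responses are few.

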6.2 Participants Taken Off Study

Patients who are enrolled but do not receive at least one dose of nivolumab or relatlimab because of noncompliance or clinical reasons will be taken off study and will receive standard treatment. These patients will not be included in the efficacy analysis and will be replaced.

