6.4 Participant Replacement Criteria

Subjects who sign the informed consent form and do not receive the study intervention may be replaced. Subjects who sign the informed consent, receive the study intervention, and subsequently withdraw, or are withdrawn or discontinued from the study due to non-compliance will be replaced by a new eligible patient.

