10 SCHEDULE OF ASSESSMENTS

10.1 Screening

Screening assessments are to be conducted within 28 days prior to initiating study unless otherwise specified. At screening, the following procedures/tests will be performed:

- Informed Consent
- Eligibility (Inclusion/Exclusion criteria)
- Demographic and medical history
- Prior and concomitant medication review
- Physical Exam
- Vital Signs: systolic and diastolic blood pressures, and temperature
- ECOG Performance Status
- 12-Lead ECG
- Echocardiogram
- Laboratory Evaluations
 - Pregnancy Test (Urine or Serum β -HCG²)
 - CBC with differential
 - Comprehensive metabolic panel
 - LDH
 - T3, free T4, TSH
 - ACTH and serum cortisol
 - Amylase
 - Lipase
 - Urinalysis
 - HBsAg, HBsAb, Hep C Ab, HB core antibody
 - Troponin T
 - PT/INR
 - PTT
- CT chest plain
- MRI brain with and without contrast
- MRI abdomen and pelvis with and without contrast (EOVIST® preferred)
- Correlative studies
 - Blood
 - Archival tissue
 - Fresh tumor biopsy if needed, safe and feasible as determined by investigator

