12.7 Progression-Free Survival

Defined as the period from the date of study entry until disease progression or death (whichever occurs first). Cases who have not had an event will be censored at the date of last disease assessment documenting the patient was free of progression. Progression will be evaluated by RECIST v1.1.

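### PFS and OS run from an undefined enrollment date while patients never dosed are removed, so the main analysis counts event-free pre-dose time and overstates both endpoints by an amount that depends on the unstated gap

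*Combined protocol and SAP*

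**What the plan says.** **Time origin.** Section 16.3 states "Progression-free survival (PFS) is defined as the time from the date of enrollment to the date that objective progression disease is documented" (or death), and "Overall survival (OS) is defined as the time from the date of enrollment to the date of death". Section 12.7 gives PFS a differently worded start: "Defined as the period from the date of study entry until disease progression or death". Neither enrollment nor study entry is tied to consent, registration or first dose.

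**Patients never dosed.** Section 6.2 covers "Patients who are enrolled but do not receive at least one dose of nivolumab or relatlimab because of noncompliance or clinical reasons". They are taken off study, and "These patients will not be included in the efficacy analysis and will be replaced". Section 6.4 is weaker on replacement: "Subjects who sign the informed consent form and do not receive the study intervention may be replaced".

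**Analysis sets.** Section 16.3 also says "The full analysis set will consist of all patients enrolled". The main efficacy set is the modified full analysis set, which leaves out patients withdrawn before the first efficacy measurement, placed at Cycle 2. Efficacy is to be repeated on the full and per-protocol sets.

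**Outputs.** For PFS and OS, Section 16.3 plans Kaplan-Meier rates at time points fixed in advance, with 95% confidence intervals. Both are secondary endpoints, and neither has a hypothesis test.

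**Screening.** Section 10.1: "Screening assessments are to be conducted within 28 days prior to initiating study unless otherwise specified".

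**The concern.** The clock starts at one event (enrollment), but a patient enters the main analysis only after a later one (first dose). A patient who dies or becomes too ill to treat between the two falls under Section 6.2 and disappears from the estimate. A patient who comes through brings the whole interval into the estimate as event-free time. This is immortal time, and it can only push PFS and OS upward.

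A single-arm trial has no control group carrying the same distortion. The disease context in Section 1.1 makes it matter more: the medians quoted there are short, so a few weeks of added time is a visible fraction of PFS. The Cycle 2 exclusion works in the same direction after first dose, if patients who die or progress early are counted as withdrawn.

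**Working it through.** **1. The plan's own figure.** The documents give no design figure for PFS or OS. The one available is the Simon design for response in Section 1.6: stop at 0/13, reject at 4 or more of 27. The rejection probability is the sum over x ≥ 1 of P(X1 = x) · P(X2 ≥ 4 − x), with X1 ~ Bin(13, p) and X2 ~ Bin(14, p). This gives 0.04159 at p = 5% and 0.80112 at p = 20%, against the stated 0.0416 and 0.8011. No time origin enters the formula, so the primary test does not depend on these clocks.

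**2. Is the pre-dose interval event-free?** Deaths: yes, by the removal rule in Section 6.2. Progression: in practice yes. Sections 10.1, 10.2 and 10.8 schedule body imaging at screening and next at Cycle 3 Day 1, so no scan falls between baseline and first dose.

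**3. Inputs for size.**
- Background medians from Section 1.1: PFS 2.6 and OS 7.6 months (PD-1/PD-L1 antibodies).
- Gap d from enrollment to first dose: not stated. Assumed range 3 to 28 days, at 30.4375 days per month.
- Exponential times, used only for rates and for the chance of an event in the gap.

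**4. Formulas.** If m is the median from first dose among dosed patients, a clock started d earlier gives m + d. The survival curve becomes S(t − d), with S(t) = 0.5^(t/m).

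| Gap | d (months) | Median PFS | Median OS | 6-month PFS | 12-month OS |
|---|---|---|---|---|---|
| none | 0 | 2.60 | 7.60 | 20.2% | 33.5% |
| 3 days | 0.10 | 2.70 (+3.8%) | 7.70 (+1.3%) | 20.7% | 33.8% |
| 7 days | 0.23 | 2.83 (+8.8%) | 7.83 (+3.0%) | 21.5% | 34.2% |
| 14 days | 0.46 | 3.06 (+17.7%) | 8.06 (+6.1%) | 22.8% | 34.9% |
| 28 days | 0.92 | 3.52 (+35.4%) | 8.52 (+12.1%) | 25.8% | 36.4% |

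For the 28-day row: 0.92/2.6 = 35%; 0.5^((6 − 0.92)/2.6) = 25.8%; 0.5^((12 − 0.92)/7.6) = 36.4%. With the other medians in Section 1.1 (immunotherapy meta-analysis, PFS 2.8 and OS 8.9 months), 28 days adds 32.9% and 10.3%.

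**5. Which rule causes it?** In a simulation with gaps uniform on 0 to 28 days, counting dosed patients only from enrollment gave medians of 3.05 (PFS) and 8.06 (OS) months. Counting dosed patients from first dose, or all enrolled patients from enrollment, each returned 2.60 and 7.60. The bias comes from combining an early clock with a late entry condition; either remedy removes it.

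**6. The Cycle 2 exclusion.** Moving the clock to first dose does not cure this. If early deaths count as withdrawn, the main set is conditioned on surviving about 4 weeks after first dose, which shifts OS as the 28-day row does. The end of that window is itself unclear, because Section 16.3 places the first efficacy measurement at Cycle 2 while the calendar places the first on-treatment scans at Cycle 3.

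**The case against.** The strongest reply is that the plan already contains the unbiased analysis. The full analysis set is everyone enrolled, and efficacy must be run on it. On its wording, that is an enrollment-based analysis with nobody removed. This stands in part: a reader might infer that no analysis keeps the undosed patients, and Section 16.3 does not support that. But the analysis is only supportive, it contradicts Section 6.2, and patients taken off study under 6.2 may have no survival follow-up to contribute.

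The second reply concerns size, and it stands. The 28 days in Section 10.1 is a window for screening assessments, not a permitted interval from enrollment to dose. Section 4.0 asks for screening labs within 10 days of treatment, and Section 4.1 mentions registration without dating it. A gap of a few days fits the text at least as well, and the effect is then small.

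Three further inferences are tempting but not supported:
- *That the plan will report inflated medians.* The planned PFS and OS outputs are rates at time points. The only median named as an endpoint is duration of response, whose clock starts at first response.
- *That the plan tests PFS and OS against history.* The historical comparison in Section 1.7.1 concerns response rates. The PFS and OS medians are background, and their time origin is not given.
- *That about a fifth of patients would progress before dosing and be deleted.* Exponential times do put 21.7% of progressions inside a 28-day gap at a 2.6-month median. With no scan scheduled then, silent progressors would ordinarily be dosed and kept.

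**Conclusion.** The point holds for the main analysis of two secondary endpoints. The direction follows from the text and is upward for both PFS and OS, whether reported as rates or as medians. The size cannot be fixed from the documents, because neither enrollment nor study entry is defined. It runs from about 4% of median PFS and 1% of median OS at 3 days to about 35% and 12% at 28 days. The upper end requires enrollment to mean consent at the start of screening.

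These figures assume the background medians in Section 1.1 and a constant gap; the rates also assume exponential times. At the same OS median, deaths inside the gap would be about 0.2 of 27 patients at 3 days and 2.2 of 27 at 28 days. Eligibility criteria on performance status and organ function probably make the true numbers lower.

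The response-rate test and the Simon stopping rule are untouched. This is a change worth making because it is cheap and removes a one-directional bias. It does not threaten the trial's primary conclusion.

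**What to change.** - In Sections 12.7 and 16.3, use one time origin for PFS and OS: the date of first dose of nivolumab plus relatlimab.
- Analyse PFS and OS in all patients who received any dose, and state that the Cycle 2 exclusion does not apply to these two endpoints. Changing the clock alone would leave that selection in place.
- Define enrollment and study entry, or use a single term.
- Reconcile Section 6.2 (and the softer replacement wording in 6.4) with the full analysis set. Undosed patients may be replaced for accrual, but should stay in an enrollment-based sensitivity analysis of everyone enrolled, with nobody removed and survival follow-up continued.

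The cost is a few sentences, a different main analysis set for PFS and OS, and survival follow-up for any undosed patients. Reported PFS and OS will be slightly shorter. Sample size and the primary analysis do not change.
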